2.3.2.2 Potential risk of desensitization therapies in patients awaiting transplantation

Desensitization therapies are immunosuppressive in nature, infection (especially cytomegalovirus [CMV] and polyoma virus) and malignancy maybe a potential risk ([33](#)). Conflicting results have been published on whether desensitization therapies such as rituximab would result in higher rate and severity of infections ([5](#), [33](#), [45](#)). A single-center retrospective study dedicated to understanding infectious complications from desensitization treatment was conducted ([46](#)). In this study, a total of 361 patients were included in the analysis. After an average of 18-month follow-up, patients who received rituximab plus IVIG for desensitization were found to have similar infection rates compared to patients who did not receive desensitization treatment. According to the authors, the infection rates observed were also similar to that reported in the literature. In a systematic review of the use of rituximab for desensitization in renal transplantation, no statistically significant higher incidence of infectious complications in patients treated with rituximab was observed ([47](#)). Lower rates of CMV viremia and viral infections were identified, and may be attributed to fewer episodes of rejection and associated steroid therapy.

A couple of publications have reported potential immunomodulatory effects of anti-CD38 mAb such as T-regulatory cell suppression and T-cell activation in multiple myeloma patients ([48](#), [49](#)). It is unknown whether these immunomodulatory effects observed in multiple myeloma patients would translate into potential concern for TCMR in patients post transplantation. While individual reports have suggested use of anti-CD38 may lead to TCMR ([41](#), [42](#)), further investigation is warranted to assess the benefit/risk ratio. Nevertheless, the main cause of kidney transplant failure is usually

attributed to AMR, which is strongly associated with graft loss, whereas TCMR was not (50, 51). It should be noted that no GVHD was observed in the clinical case that reported the use of daratumumab to desensitize a patient who received ABO-mismatched stem cell transplantation (43).

2.3.3 Preventive measures to minimize the risk of isatuximab

To minimize the risk of IRs, all participants treated with isatuximab should routinely receive primary prophylactic treatment with diphenhydramine 25 to 50 mg IV (or equivalent), methylprednisolone 100 mg IV (or equivalent), acetaminophen (paracetamol) 650 to 1000 mg orally (or equivalent), and montelukast 10 mg orally (or equivalent), approximately 15 to 30 minutes (and never longer than 60 minutes) prior to the isatuximab infusion to minimize the incidence and severity of IR commonly observed with certain mAbs. It is recommended that prescribing information of each of these medications to be considered in the context of each patient's clinical situation.

In an attempt to further mitigate the incidence and severity of IRs, infusion of isatuximab is administered in a titrated manner (see [Section 6.1](#)). In the event of a mild or moderate hypersensitivity reaction, the isatuximab infusion should be interrupted and may subsequently resume after recovery, at a slower infusion rate, under close monitoring and with supportive care as needed. Prior to restarting the infusion, participants may receive additional medication per the judgment of the Investigator; recommended medications consist of diphenhydramine 25 mg IV and methylprednisolone 100 mg IV (or equivalent). In the event of a severe hypersensitivity reaction, treatment with isatuximab is to be immediately and permanently discontinued. Detailed management guidelines for IRs are also provided in [Section 6.6.4](#).

Isatuximab infusion administered in units of mL per hour has been evaluated in Study TCD14079 Part B. A total of 47 patients were included in this study. The primary endpoint of the study was achieved as no Grade ≥ 3 IRs were reported, therefore confirming the feasibility of the fixed volume infusion method of isatuximab administration. The overall incidence of IRs was 40.4%.

For the risk of neutropenia and infections, Investigators are recommended to monitor complete blood cell counts periodically during the treatment. Antibiotics, antifungal, and antiviral prophylaxis can be considered during the treatment. Patients with neutropenia should be monitored for signs of infection. No dose reductions of isatuximab are recommended. Dose delays and the use of colony stimulating factors (eg, granulocyte-colony stimulating factor [G-CSF]) may be required to allow improvement of neutrophil count.

To mitigate potential risk of infections in patients receiving isatuximab, participants with active, recurrent, or chronic infections requiring treatment are excluded from the study. Furthermore, participants with positive hepatitis core antigen but hepatitis B surface antigen (HBsAg) negative must receive prophylactic antiviral therapy prior to IMP initiation, and should continue therapy until end of site visit FUP or early discontinuation. Potential viral reactivation (including hepatitis B virus [HBV], CMV, and Epstein-Barr virus [EBV]) in participants will be monitored pre- and post-treatment with isatuximab.

To avoid potential problems with blood transfusion, the American Association of Blood Banks recommends that patients being treated with anti-CD38 antibodies have blood type and screen

tests performed prior to treatment (ie, at screening see [Section 1.3](#)). After the treatment and each time before blood transfusion, the antibody screen test (indirect Coombs test) should be performed. After a patient begins taking anti-CD38 antibodies, ABO/RhD typing can be performed normally; for antibody detection and identification, dithiothreitol (DTT)-treated cells can be used to eliminate the interference (see [Section 10.10](#) for details).

In regard to the aforementioned potential risk of TCMR, participants who received isatuximab and subsequently proceed to solid organ transplantation are recommended to receive anti-thymocyte globulin (as indicated for prophylaxis of acute rejection) and steroids maintenance as part of the post-transplant immunosuppression regimen. During extended FUP, post-transplant status including rejection episodes and graft survival will be collected.

Additionally, careful monitoring of AEs and laboratory abnormalities, continuous direct communication between the Investigators and the monitoring team, and the adherence to the dose modification rules specified in the study protocol, are the continuous measures that will minimize the risks in study participants.

Overall, the anticipated benefit/risk ratio of isatuximab supports the conduct of study TED16414 in participants diagnosed with CKD awaiting kidney transplantation.

More detailed information about the known and expected benefits and risks and reasonably expected AEs of isatuximab may be found in the Investigator's Brochure.

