1.3 SCHEDULE OF ACTIVITIES (SOA)

Procedure	Screening (up to 28 days before Day 1)	Treatment Period (12 weeks)								Site Visit FUP (26 weeks) ^a	E/D ^b	Extended FUP ^c	Notes All on-treatment procedures should be performed prior to IMP administration unless indicated otherwise				
		Cycle 1 (28 Days)				Cycle 2 (28 days)		Cycle 3 (28 days)									
		D1	D8	D15	D22	D1	D15	D1	D15								
Time Window (days)		±1	±1	±1	±1	±2	±2	±2	±2	±7	±7	±7					
Informed consent	X												Informed consent may be signed prior to D- 28				
Inclusion and exclusion criteria	X																
Demography	X												Date or year of birth (depending on local regulation), sex, ethnicity, and race (if local regulation allows)				
Medical, disease, and surgical history	X												Include start date of dialysis				
Sensitizing events	X	←=====→											Collect dates and types of relevant sensitizing events that can impact cPRA (eg, Blood transfusion)				
HLA tissue typing (collect data on already available results is acceptable)	X												For screening (can be done prior to D-28), enter the most recent results if available				
12-lead ECG	X												See Section 8.2.3				

Procedure	Screening (up to 28 days before Day 1)	Treatment Period (12 weeks)								Site Visit FUP (26 weeks) ^a	E/D ^b	Extended FUP ^c	Notes All on-treatment procedures should be performed prior to IMP administration unless indicated otherwise				
		Cycle 1 (28 Days)				Cycle 2 (28 days)		Cycle 3 (28 days)									
		D1	D8	D15	D22	D1	D15	D1	D15								
Time Window (days)		±1	±1	±1	±1	±2	±2	±2	±2	±7	±7	±7					
Echocardiography	X												Should be performed at dry weight, and/or on a non-dialysis day (see Section 8.2.4)				
Full physical examination including height (screening only) and weight	X (≤7 days prior to first IMP)	X		X		X		X		X (Weeks 1 and 9 only)	X		See Section 8.2.1				
Vital signs ^d	X	X	X	X	X	X	X	X	X	X (Weeks 1 and 9 only)	X		See Section 8.2.2)				
Pregnancy test (WOCBP)	X (≤7 days prior to first IMP)					X		X		X ^e (Week 1, and 5 months after last dose)	X ^e		Serum pregnancy test at screening; serum or urine hCG pregnancy test at other time points See Section 10.2				
HBV, HCV, HIV, CMV, EBV	X	As clinically indicated								X ^f	X ^g		See Section 10.2				
Laboratory assessments (blood chemistry, hematology)	X (≤14 days prior to first IMP)	X ^h		X		X		X		X (Weeks 1 and 9 only)	X		See Section 10.2				

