Prior/concomitant/post medication ^m	X	←=====→								X	X	X	See Section 6.5				
Participant/Transplant (if applicable) Status	X ⁿ	X ⁿ								X ^o	X ^o						

Abbreviations: ADA = anti-drug antibody, AE = adverse event, CMV = cytomegalovirus, cPRA = calculated panel reactive antibodies, D = Day, EBV = Epstein-Barr virus, ECG = electrocardiogram, E/D = early discontinuation, FUP = follow-up period, HBV = hepatitis B virus, hCG = human chorionic gonadotropin, HCV = hepatitis C virus, HIV = human immunodeficiency virus, HLA = human leukocyte antigen, ID = identification number, IMP = investigational medicinal product, MFI = mean fluorescence intensity, PK = pharmacokinetics, SAB = single antigen bead, SoA = Schedule of Activities, SAE = serious adverse event, WOCBP = women of childbearing potential.

- a Week 1 visit for site visit FUP will occur 15 days after Cycle 3 Day 15 (± 7 days), or 15 (± 7 days) after the last dose of IMP if participant discontinued IMP. Depending on local arrangements and preference of the Investigator, site visit FUP procedures may be performed at the study site or at the participant's home by a health care professional. Study procedures not performed at the study site must also be documented in the source documents and recorded in the appropriate pages of the eCRF by the study site.
- b For E/D, study procedures will be performed 30±7 days after last IMP administration if discontinued study during treatment period, or within 30 days if discontinued during site visit FUP. Participants who discontinued IMP but remain on the study and proceed to complete site visit FUP do not need to complete E/D. Participants who wish to proceed to transplantation when a compatible donor becomes available while on study must discontinue IMP immediately, and complete an E/D visit prior to transplantation if clinically feasible, and proceed to extended FUP.
- c In addition to the phone calls every 90 days, study site will collect information per the SoA throughout the extended FUP.
- d Vital sign assessment includes blood pressure, pulse rate, temperature, and respiratory rate. During the treatment period, vital signs should be obtained prior to start of each IMP infusion, 1 hour after start of infusion, at the end of infusion, and during the infusion if clinically indicated.

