- e Pregnancy test can be performed at home for participants during the FUP or if date of test does not match with FUP visit and the site must record this in the source document. Test should be performed at the end of isatuximab treatment (ie, Week 1 of site visit FUP or E/D visit [± 7 days]), and 5 months (± 7 days) after the last dose of IMP.
- f Post-treatment tests are only applicable for HBV, CMV, and EBV, and only has to be performed at Site Visit FUP Week 9 if baseline result is positive or as clinically indicated. In case HBV vaccination will be started before first study treatment administration, anti-HBs should be monitored at approximately 1, 2, and 3 months after end of vaccination (± 7 days, or at the next blood sampling). For participants with positive anti-HBc and negative HBsAg and undetectable HBV deoxyribonucleic acid (DNA) at study entry (past resolved infection, resolving acute infection, or receiving antiviral treatment with controlled infection), close monitoring of viral reactivation (greater than 1log10 IU/mL increase in HBV DNA or reappearance of HBsAg or detection of HBV DNA in patients with resolved infection) throughout and following the end of study

treatment should be proposed (alanine aminotransferase [ALT], aspartate aminotransferase [AST], and HBV DNA at Site Visit FUP Week 9 and Week 25, or until initiation of further desensitization therapy/transplant surgery). In case of viral reactivation during study treatment (greater than 1log10 IU/mL increase in HBV DNA or reappearance of HBsAg or detection of HBV DNA in participants with resolved infection), close monitoring of ALT and AST approximately every month (may coincide with the next scheduled blood sampling \pm 7 days), up to study treatment discontinuation. HBV DNA to be done as per Investigator's and/or specialist advice.

- g Only if screening result is positive and not tested during site visit FUP.
- h Assessment not required to be repeated prior to Cycle 1 Day 1, if screening assessments were performed within 7 days prior to the first IMP infusion and met the entry criteria. Window for assessment is within 1 working day prior to IMP infusion.

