5.2 EXCLUSION CRITERIA

Participants are excluded from the study if any of the following criteria apply:

Medical conditions

E 01. Known malignancy requiring active treatment within 3 years prior to IMP initiation, with the exception of complete resection of basal cell carcinoma or squamous cell carcinoma of the skin, an in situ malignancy, or low-risk prostate cancer after curative therapy.

E 02. History of significant cardiac dysfunction such as New York Heart Association classification for chronic heart failure III-IV, symptomatic cardiovascular disease, major clinically significant electrocardiogram (ECG) abnormality, left ventricular ejection fraction <40%, clinically significant ventricular arrhythmias, myocardial infarction within 6 months prior to IMP initiation, or unstable or poorly controlled angina pectoris despite treatment.

E 03. In the opinion of Investigator, participant with severe autonomic dysfunction leading to chronic hypotension.

E 04. Evidence of active mucosal or internal bleeding.

E 05. History of 2 or more events of pulmonary embolism or deep-vein thrombosis.

E 06. Known active, recurrent or chronic infection requiring parenteral or oral anti-infective treatment; including primary or secondary immunodeficiency, a history of active or latent

tuberculosis or history of deep tissue/space infection (peritoneal, etc) within 24 weeks prior to IMP initiation, or any serious infection within 8 weeks prior to IMP initiation.

- E 07. Participants on peritoneal dialysis with a history of peritoneal infection at any time during the 12 weeks prior to IMP initiation.
- E 08. Participants on peritoneal dialysis with a positive culture or high cell count numbers on peritoneal fluid indicative of confirmed or suspected infection at the time of screening.
- E 09. Known active hepatitis B or C viral infection, or human immunodeficiency virus (HIV).
 - Participants with positive hepatitis B core antigen (anti-HBc or HBcAb) but HBsAg negative who received prophylactic antiviral therapy prior to IMP initiation are eligible and should continue therapy until end of treatment period or E/D visit. Participants with negative HBsAg and positive HBV deoxyribonucleic acid (DNA) observed during screening period will be evaluated by a specialist or Investigator for start of antiviral treatment: study treatment could be proposed if HBV DNA becomes negative and all the other study criteria are still met.

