HBV vaccination could be considered, following investigator's discretion, for patients with negative HBsAg, total anti-HBc, anti-HBs and HBV-DNA. At least 3 doses of vaccine will be administered at monthly intervals, the first one 1-2 weeks before start of study treatment. Anti-HBs should be monitored at approximately 1, 2 and 3 months after end of vaccination (± 7 days, or at the next blood sampling). Anti-HBs above 100 mU/mL will indicate a good seroconversion, between 10 and 100 mU/mL moderate seroconversion that can be limited in time, less than 10 mU/mL will indicate no response to vaccination.

If antiviral therapy for HBV or HCV was started before initiation of IMP and patient was eligible for the trial, the antiviral therapy for HBV or HCV should continue throughout the treatment period as recommended by specialist or Investigator.

See [Section 6.6.3](#) in case of hepatitis B viral reactivation (sub section "Guidance in case of hepatitis B reactivation occurring under study treatment").

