10.12.1 Amended protocol 01 (23 July 2020)

This amended protocol 01 (amendment 01) is considered to be substantial based on the criteria set forth in Article 10(a) of Directive 2001/20/EC of the European Parliament and the Council of the European Union.

OVERALL RATIONALE FOR THE AMENDMENT

Protocol amendment summary of changes table

Section # and Name	Description of Change	Brief Rationale
1.1 Synopsis; 2.3.3 Preventive measures to minimize the risk of isatuximab; 6.1 Study intervention(s) administered	Ranitidine is removed from standard premedication regimen and will be considered as per medical judgement of the Investigator. Criteria for optional premedication is simplified to base on no IR upon 4 consecutive infusions.	To provide option to adapt the premedication depending on individual situation.
1.3 SoA (footnote f); 5.2 Exclusion criteria; 6.5 Concomitant therapy; 6.6.3 General guidelines for the management of adverse events; 10.2 Appendix 2 Clinical laboratory tests	Included detailed guidance relating to viral reactivation monitoring and risks. As a new footnote "f" was implemented, numbering of following footnotes were shifted accordingly.	To clarify monitoring and risks related to viral reactivation.
1.3 SoA (footnote i)	Added indirect Coombs tests after treatment period during Site Visit follow-up period (FUP) if C2D1 is positive.	To investigate duration of blood typing interference following termination of isatuximab treatment.
1.3 SoA (Blood draw for functional immune cell assay)	Add sample collection during Site Visit FUP Week 1 or E/D if C3D1 sample not collected.	To ensure a post-treatment sample is collected in case C3D1 sample is not collected or if patient discontinued treatment prior to C3D1.
1.3.1.1 Treatment period: Cycle 1 (rich sampling)	C1D1 EOI+4h (\pm 30 min) timepoint is modified to EOI+1h (+30 min) timepoint.	Modification of sample collection timepoint to reduce wait time/burden for study participants.
1.3.1.1 Treatment period: Cycle 1 (rich sampling) 1.3.1.2 Treatment period: Cycle 2 and beyond (sparse sampling)	Addition of allowing PK/ADA sample to be collected at participant's home by a health care professional (depending on local arrangements).	To provide flexibility and potentially reduce site visit for study participants.
2.2 Background	Updates of isatuximab approval status and number of treated patients.	To provide updates aligned with updates of isatuximab IB ed11.

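### Protocol Section 2.3.3 and exclusion criterion E09 give different ends for hepatitis B antiviral prophylaxis in the same participants, up to 26 weeks apart

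*Protocol*

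**What the plan says.** Four places in the protocol bear on how long HBV antiviral cover lasts. The SAP does not address it.

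- **Section 2.3.3 (preventive measures).** Anti-HBc-positive, HBsAg-negative participants "must receive prophylactic antiviral therapy prior to IMP initiation, and should continue therapy until end of site visit FUP or early discontinuation".
- **Section 5.2, E09.** The same participants are eligible if prophylaxis was started before the study drug, and they "should continue therapy until end of treatment period or E/D visit".
- **Section 6.5 (concomitant therapy).** Where antiviral therapy was started before the study drug, "the antiviral therapy for HBV or HCV should continue throughout the treatment period as recommended by specialist or Investigator".
- **Section 1.3, Schedule of Activities, footnote f.** For participants with this serology and undetectable HBV DNA at entry, it proposes ALT, AST and "HBV DNA at Site Visit FUP Week 9 and Week 25, or until initiation of further desensitization therapy/transplant surgery". It sets monitoring and says nothing about when prophylaxis stops.

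**The concern.** Sections 2.3.3 and 5.2 describe the same people and the same drug treatment, yet one runs the prophylaxis through follow-up and the other ends it with dosing. A site is more likely to work from the eligibility criteria than from the benefit/risk narrative, so E09 may be the text it applies.

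The longer duration is one of the infection mitigations listed in Section 2.3.3 ahead of its benefit/risk conclusion. If sites apply E09, the mitigation delivered is shorter than the one described. The protocol itself treats the months after dosing as relevant: Section 2.3.2.1 names opportunistic infection as an identified risk, and footnote f keeps HBV monitoring going into follow-up Week 25.

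**Working it through.** No sample-size or power formula is involved. The check is a comparison of texts and a day count.

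**Inputs**
- Screening up to 28 days, treatment up to 12 weeks, site visit follow-up (FUP) up to 26 weeks (Section 4.1).
- Three 28-day cycles, last planned infusion on Cycle 3 Day 15 (Section 1.3).
- "Week 1 visit for site visit FUP will occur 15 days after Cycle 3 Day 15", with a ±7-day window (Section 1.3, footnote a).
- HBV DNA at FUP Weeks 9 and 25 (footnote f).
- The PK/ADA flowchart in Section 1.3.1.2 labels the FUP Week 9 visit D60.

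**1. Reproduce the plan's own figure.** 4 + 12 + 26 = 42 weeks. This matches the stated site-visit duration of approximately 42 weeks.

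**2. Locate the two ends, assuming no delays and first dose on Day 1.**

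| Event | Calculation | Study day | Days after last infusion |
|---|---|---|---|
| Last infusion (C3D15) | 56 + 15 | 71 | 0 |
| End of treatment period (E09) | 3 × 28 | 84 | 84 − 71 = 13 |
| End of site visit FUP (2.3.3) | 84 + 26 × 7 | 266 | 266 − 71 = 195 |

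Gap: 266 − 84 = 182 days = 26 weeks. This is a maximum, because follow-up is up to 26 weeks.

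**3. Scheduled checks after a stop on Day 84.**
- FUP Week 1 (routine chemistry, including ALT and AST): 71 + 15 = Day 86, 2 days after the stop. With the ±7-day window this is 5 days before to 9 days after, so it can precede the stop.
- FUP Week 9 (first scheduled HBV DNA) depends on the anchor, which the protocol does not state:
  - If D60 counts from the last dose: 71 + 60 = Day 131, and 131 − 84 = 47 days after the stop (40 to 54 with the window).
  - If Week 9 is 8 weeks after the Week 1 visit: 86 + 56 = Day 142, and 142 − 84 = 58 days after the stop (51 to 65 with the window).
- FUP Week 25, on the second anchor: 86 + 168 = Day 254, 170 days after the stop.

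**4. Does any other text decide between the two ends?**
- Section 6.5 requires cover during treatment and defers to the specialist or Investigator. That is compatible with stopping at Day 84 or continuing to Day 266.
- Footnote f is also compatible with both. Monitoring after treatment makes sense whether or not prophylaxis continues.

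**The case against.** The case for leaving this alone is mostly about weight, and much of it stands.

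- **Neither text orders a stop.** Both say *should continue*, so a site that carries on to the end of follow-up complies with both. This is correct, and it limits the consequence.
- **The operative sections lean one way.** E09 and Section 6.5 both name the treatment period, while Section 2.3.3 is narrative. This is a fair lean, but Section 6.5 also fits longer therapy and defers to clinical judgement, so it does not resolve the conflict.
- **Other safeguards remain.** Active hepatitis B is excluded, routine ALT and AST are drawn at FUP Week 1, and HBV DNA, ALT and AST are proposed at Weeks 9 and 25. This also stands.

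Three stronger readings are tempting, and the documents do not support them.

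- **That the shorter end was a deliberate change.** The Amendment 01 log (Section 10.12.1) lists Sections 5.2 and 6.5, but not 2.3.3, under "Included detailed guidance relating to viral reactivation monitoring and risks". The entry does not mention prophylaxis duration or show which words of E09 changed, so it cannot establish intent.
- **That the two texts also conflict for participants who leave during treatment.** For them the early discontinuation (E/D) visit falls 23 to 37 days after the last dose ("study procedures will be performed 30±7 days after last IMP administration if discontinued study during treatment period"). A difference of up to 37 days arises only if the phrase in Section 2.3.3 means the event rather than the visit. The synopsis uses the term for the visit, and on that natural reading there is no difference.
- **That participants will be harmed.** The documents give neither the number of anti-HBc-positive participants nor a reactivation risk after stopping.

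**Conclusion.** The contradiction is real. Two current sections give the same participants different ends for HBV prophylaxis, and nothing in the documents settles which was meant. For those who complete follow-up the ends differ by up to 26 weeks: about 13 versus up to 195 days after the last infusion. Under the shorter end, the first scheduled HBV DNA check comes roughly 47 to 58 days after the stop.

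The day counts assume three cycles without delay and full follow-up. The Week 9 range rests on the two possible anchors for that visit. The number affected is probably small, since total enrolment is about 24 to 42, but that is an inference, and harm cannot be quantified. This is an internal inconsistency in a safety instruction and a minor correction, with no bearing on sample size, power or the primary analysis.

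**What to change.** Change E09 so that prophylaxis runs *to the end of site visit FUP or the E/D visit*. This matches Section 2.3.3 and satisfies both texts. If the sponsor's clinical team confirms that the shorter end was intended, correct Section 2.3.3 instead. In either case, read early discontinuation in Section 2.3.3 as the E/D visit.

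Any edit to Section 6.5 should cover HBV prophylaxis only and keep the specialist or Investigator role. The same sentence also governs hepatitis C therapy, which has its own end in E09 (seroconversion), and that instruction should not change. Footnote f needs no change.

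The cost is a line or so of text, by clarification letter or in the next amendment. The clinical downside of the longer end is up to 26 more weeks of antiviral therapy for a probably small number of participants.
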